5.2.5.2 Specific modifications

It is decisive for dose modification, whether the toxicities occur

- 1. on the day of the oxaliplatin iv. application or
- 2. during the 5-FU infusion or
- 3. on another day of the treatment course

If a toxicity occurred during the interval between the chemotherapy courses, the drug dose in the subsequent course will be adapted according to the following table:

CTC grade	1	2	3	4
WBC	100%	100%	5-FU: 75%	5-FU: 75% L-OHP: 75%
Platelets	100%	100%	5-FU: 75%	5-FU: 75% L-OHP: 75%
Mucositis	100%	100%	5-FU: 75%	5-FU: 75% L-OHP: 75%
Diarrhea	100%	100%	5-FU: 75%	5-FU: 75% L-OHP: 75%
Skin	100%	100%	5-FU: 75%	Off treatment

If one of the following toxicity findings is still present on the day of the next chemotherapy administration:

- Diarrhea > grade 1
- Mucositis > grade 1
- Leukopenia > grade 2
- Thrombocytopenia > grade 1
- Other toxicities > grade 2

therapy has to be delayed for at least one week, and started when WBC have risen to > $3000/\mu$ I and platelets to > $100.000/\mu$ I and gastrointestinal toxicities have resolved. If necessary, a delay for a second week is allowed.

The following dose adjustments have to be undertaken in case of neurotoxicity caused by oxaliplatin:

Duration of toxicity			
	1-7 days	> 7 days	Persisiting durimng the chemotherapy interval
Cold related dysaesthesia	No change	No change	No change
Paraesthesia	No change	No change	Reduce by 25%
Paraesthesia with pain	No change	Reduce by 25%	stop L-OHP continue 5-FU
Paraesthesia with functional impairment	No change	Reduce by 50%	stop L-OHP continue 5-FU

In a small number of patients a special form of acute neuropathy, laryngopharyngeal dysaesthesia syndrome, may occur with a subjective feeling of dysphagia and dyspnoea but without objective signs of airway obstruction. This syndrome is not life-threatening and rapidly reversible without any treatment. During the following cycles the duration of infusion should be prolonged to 6 hours.

The specific neurotoxicity caused by oxaliplatin is recorded according to the following scale developed by Wassermann et al.:

Grade 1	Paraesthesia/Dysaesthesia < 7 days
Grade 2	Paraesthesia/Dysaesthesia 8-14 days
Grade 3	Paraesthesia/Dysaesthesia > 14 days
Grade 4	Paraesthesia/Dysaesthesia with functional impairment

5.3 RADIOTHERAPY

5.3.1 Description

No prior pelvic irradiation:

Patients undergo radiotherapy once daily, 5 days a week, for 5 weeks. Patients receive 45 Gy (25 x 1.8 Gy) to the pelvis (ICRU-report 50). The pelvic radiotherapy uses a three or four field box technique and at least 6 MV photon beams. The field borders for pelvic irradiation are confined as follows:

Patients with tumors that are considered as not resectable after 45 Gy receive a 3Dconformal boost to the gross tumor volume with a security margin of 1-2 cm in every direction to a total dose of 59.8 Gy, at least. Patients with tumors that are considered as resectable receive surgery in curative intention 4-6 weeks after completion of chemoradiation.

Prior pelvic irradiation:

Patients undergo 3D-conformal radiotherapy once daily, 5 days a week, for 5 weeks. Patients receive 45 Gy (25 x 1.8 Gy) to the gross tumor volume with a security margin of 1-2 cm in each direction (ICRU-report 50). Radiotherapy uses 6 MV photon beams, at least.

Patients with tumors that are considered as not resectable after 45 Gy receive a 3Dconformal boost to the gross tumor volume with a security margin of 1-2 cm in every direction. The total dose is left to the discretion of the local radiotherapist. Patients with tumors that are considered as resectable receive surgery in curative intention 4-6 weeks after completion of chemoradiation.

5.3.2 Modifications in case of toxicity

In case of acute diarrhea or hemorrhagic cystitis grade 4 during treatment, radiotherapy will be withheld until resolution of symptoms. When radiotherapy is withheld, chemotherapy and hyperthermia will not be delivered. RT will also be withheld for WBC <1.0 x 10^{9} /l, neutrophil count < 0.3 x 10^{9} /l and/or platelet count < 20 x 10^{9} /l. If the treatment delay exceeds two weeks, the patient goes off protocol treatment and the end-of-treatment document page is reported.

5.4 DEEP REGIONAL HYPERTHERMIA

5.4.1 Description

Hyperthermia is scheduled twice weekly during the time of external radiotherapy and started within one hour before or after irradiation to a total of 10 treatments. The interval between two RHT-treatments has to be a minimum of 72 hours. Thermometry probes have to be positioned in the rectum (if accessible), the bladder, the vagina and the rima ani for continuous thermometry and thermal mapping of tumor-related temperatures. Therapeutic time starts when the tumor-related temperature in the rectum reached a minimum of 41.5°C or 30 min after enabling power. Therapeutic time is scheduled to be 60 min, the maximum total duration should not exceed 90 min.

Maximum bladder and vagina temperatures should not exceed 43°C. In the event that bladder temperature exceeds 43°C irrigation of the bladder with a cool saline solution may be carried out to reduce bladder temperature without necessarily decreasing power. Systemic body temperature (measured orally) should not exceed 39°C. In the event of systemic temperature rising above this level, cooling of the patient should be attempted with fans, cool water, etc. before decreasing power.

Power should be adjusted for heart rate and/or blood pressure changes at the discretion of the individual institution.

5.4.2 Modifications in case of toxicity

In case of small volume first-, second-, or third-degree burns (<3 cm in greatest dimension) generally no adjustment is necessary. Therapy may be continued at the discretion of the attending physician unless pain is prohibitive. In the case of subcutaneous burns (i.e. subcutaneous nodules or fat necrosis) therapy may generally be continued unless prohibitive pain dictates discontinuance at the discretion of the attending physician.

Radiotherapy or chemotherapy will not be withheld in the event that hyperthermia has to be withheld. In the event that chemotherapy must be withheld, radiotherapy and hyperthermia will not necessarily be withheld unless the specific criteria for dose modification are met. No hyperthermia will be delivered after the conclusion of radiotherapy, even if one or more hyperthermia treatments were skipped.

5.5 SURGICAL THERAPY

4-6 weeks after chemoradiation, tumour resection should be performed if possible and if no contraindications are present. Contraindications may be infiltration of the sacral vertebras 1 and 2 or infiltration of the basal pelvic muscles. The definite decision on further surgical treatment is left to the discretion of the local surgeon.

All surgical procedures should be performed according to the local standards of the invstigator's institution, according to established guidelines and recommendations. Surgery is not considered as an integral part of the experimental study treatment.

5.6 CONCOMITANT AND SUPPORTIVE TREATMENT

5.6.1 General aspects

In general, the patients should continue to take their previous therapies according to the recommendations of the responsible physician. The following concomitant therapies will not be allowed:

- any other antineoplastic treatment
- other investigational therapies
- initial prophylactic use of G-CSF, GM-CSF and other growth factors

Concomitant medication, which is relevant for the study assessments, have to be recorded. Additionally, any diagnostic, therapeutic or surgical procedure performed during the study period should be recorded.

Supportive care for treatment-related symptoms will be offered as needed to all patients in this study.

5.6.2 Treatment of nausea/vomiting

For acute nausea and vomiting, a 5-HT3 antagonist with corticosteroids prior to infusion would be considered standard premedication for oxaliplatin. For delayed nausea and vomiting, an oral 5-HT3 antagonist is the first option; metoclopramide, alizapride and prochlorperazine may be also used.

5.6.3 Treatment of diarrhea

A prophylactic treatment is not recommended. As soon as signs of diarrhea occur, the patient should immediately consult his physician and start with the intake of loperamide: 2 capsules (4 mg), thereafter 1 capsule (2 mg) every two hours, for at least 12 hours and for at least 12 hours after the last observation of liquid stool, up to a maximum treatment duration of 48 hours. The use of drugs with laxative properties should be avoided because of the potential for exacerbation of diarrhea. Patients should be advised to contact their physician to discuss any laxative use. Sufficient oral rehydration has to be administered during the whole diarrhea episode.

If diarrhea is severe (requiring intravenous rehydration) and/or associated with fever or severe neutropenia (Grade 3 or 4), broad-spectrum antibiotics must be prescribed. Patients with severe diarrhea or any diarrhea associated with severe nausea or vomiting or prolonged diarrhea (> 48 h despite loperamide treatment) **must be hospitalized** for intravenous hydration and correction of electrolyte imbalances.In case of persisting severe diarrhea despite loperamide treatment, this drug should be replaced by another antidiarrheic therapy (e.g. octreotide).

5.6.4 Prevention and treatment of neutropenia

In case of severe neutropenia patients undergo a high risk of developing infections and/or febrile neutropenia, especially if diarrhea occurs simultaneously. As soon as an asymptomatic grade 4 neutropenia or a febrile neutropenia (grade 3 or 4) is recorded, the dose of future chemotherapy applications has to be modified (cf. section 5.2).

Prophylactic treatment with antibiotics is not recommended, even in case of grade 4 neutropenia (without fever or diarrhea), but the decision is up to the local investigator's preference. Prophylactic hematopoietic growth factors (i.e., G- or GM-CSF) are not recommended, but secondary prophylaxis after a previous episode of neutropenia is up to the discretion of the investigator. Use of any supplementary growth factor must be documented in the patient record. Growth factors must be discontinued at least 48 hours prior to initiation of the next cycle of chemotherapy.

5.7 EMERGENCY MANAGEMENT

In case of an emergency the coordinating investigator can be approached via the following phone/fax connection:

[name] (LKP) Univ. Hospital Erlangen Dept. of Radiation Oncology [name] [name] Germany [contact] [contact] Email: [contact]

Serious adverse events or reactions (cf. section 6.7.3 and 6.7.4), observed during the conduct of the study, have to be reported to the coordinating investigator/sponsor within 24 hours. A specific SAE form has to be filled.

5.8 **PREMATURE WITHDRAWAL OF AN INDIVIDUAL SUBJECT**

Patients will be removed from protocol treatment for the following reasons:

- disease progression,
- development of unacceptable toxicity
- treatment delay more than three weeks
- administration of any other anti-neoplastic medication or any other experimental drug
- consent withdrawn
- investigator decision in the best interest of the patient

- pregnancy or insufficient contraception
- loss to follow-up
- death

The time point of and reason for removal of a patient must be documented on the case report form. The investigator will attempt to complete all discharge procedures at the time a patient is discontinued from study treatment and to record further follow-up data, if required.

5.9 **PREMATURE STUDY TERMINATION BY THE SPONSOR/COORDINATING INVESTIGATOR**

At any time, the sponsor/coordinating investigator of the study may terminate the trial participation of an individual patient, as well as the whole trial, provisionally or permanently, if this is required by stringent medical, administrative or legal reasons (including insufficient patient recruitment), especially if severe and/or frequent adverse events occur, requiring a new risk/benefit evaluation.

6 STUDY ASSESSMENTS AND CRITERIA OF EVALUATION

STUDY PARAMETERS	pre-study	day 1, 9, 16, 23, 30	on day 9 + 23, additionally	end of treat- ment, day 35	post- surgery (if possible)	follow- up ⁶
Informed consent	X ¹					
History	X ¹					
Physical exam	X ²	Х		Х	Х	Х
Vital Signs	X ²	Х		Х	Х	
Neurological exam	X ²		Х	Х		Х
Height	X ²					
Body weight	X ²	Х				
Performance status	X ²			Х	Х	Х
ECG	X ¹			X ⁵		
Pregnancy test	X ^{1,4}					
CBC/differential blood count ⁷	X ²	Х		Х		
Serum chemistry ⁸	X ²	Х		Х		
CEA	X ²					
Toxicity/symptoms (NCI CTC)	X ²	Х		Х	Х	х
Tumor assessment	X ³			Х	Х	Х
Chest X ray	X ³			X ⁵		X ⁵
Endosonography	X ³					
Rektosigmoidosc./ coloscopy	Х ³			Х		
CT of abdomen	X ³			Х		Х
Pathology	X ³				Х	

6.1 OVERVIEW / SCHEDULE OF STUDY ASSESSMENTS

- 1. Within 14 days prior to the start of therapy.
- 2. Within 7 days prior to the start of therapy.
- 3. Within 21 days prior to the start of therapy.
- 4. In case of women with child-bearing potential.
- 5. As clinically indicated.
- 6. Every 3 months for 2 years, thereafter every 6 months for 3 additional years
- 7. Hb, WBC, granulocytes, platelets
- 8. Sodium, potassium, calcium, creatinine, urea, bilirubin, GOT, GPT, LDH, alk. phosphatase, total protein, albumin.

6.2 ASSESSMENTS AT RECRUITMENT

The following baseline assessments will be conducted or obtained within two weeks prior to start of study treatment unless otherwise indicated:

- Signed written informed consent.
- Complete medical history including dates and description of initial diagnosis of rectal cancer, pre-treatment, documentation and measurement of all measurable and/or non-measurable lesions, tumor related symptoms, relevant concurrent illnesses and relevant concomitant medication.
- Physical examination including: weight, height, WHO performance status (appendix 2), and complete neurological examination within 7 days prior to treatment.
- Vital signs: blood pressure, pulse rate and oral temperature within 7 days prior to treatment.
- Residual toxicities from prior therapies should be recorded using the NCI Common Toxicity Criteria (appendix 3).
- 12 lead ECG.
- Hematological tests: Complete blood count (CBC) including neutrophil and platelet count.
- Clinical chemistry: Sodium, potassium, calcium, creatinine, urea, bilirubin, GOT, GPT, LDH, alk. phosphatase, total protein, albumin
- Tumor marker (CEA).
- Urine or serum HCG if patient is of childbearing potential.
- Chest X ray within three weeks prior to treatment.
- Endosonography within three weeks prior to treatment.
- Rectosigmoidoscopy/coloscopy within three weeks prior to treatment.
- CT scan of the abdomen

The above tests and procedures are summarized in the Study Flow Sheet in section 6.1.

6.3 ASSESSMENTS DURING AND AFTER STUDY TREATMENT

On day 1, 9, 16, 23, 30 of radiochemotherapy:

- Physical examination, vital signs, performance status
- Hematological tests: Complete blood count (CBC) including neutrophil and platelet count.
- Clinical chemistry: Sodium, potassium, calcium, creatinine, urea, bilirubin, GOT, GPT, LDH, alk. phosphatase, total protein, albumin
- Toxicity assessment according to NCI CTC (cf. appendix 3)

In addition, on day 9 and 23:

• Neurological examination

At the end of radiochemotherapy (day 35):

- Physical examination, vital signs, performance status
- Neurological examination
- 12 lead ECG (if clinically indicated).
- Hematological tests: Complete blood count (CBC) including neutrophil and platelet count.
- Clinical chemistry: Sodium, potassium, calcium, creatinine, urea, bilirubin, GOT, GPT, LDH, alk. phosphatase, total protein, albumin
- Toxicity assessment according to NCI CTC (cf. appendix 3)
- Tumor assessment by imaging techniques, corresponding to those used at baseline. Additional tumor assessments, if clinically indicated.

The above tests and procedures are summarized in the Study Flow Sheet in section 6.1.

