Patients with tumors that are considered as not resectable after 45 Gy receive a 3D-conformal boost to the gross tumor volume with a security margin of 1-2 cm in every direction. The total dose is left to the discretion of the local radiotherapist. Patients with tumors that are considered as resectable receive surgery in curative intention 4-6 weeks after completion of chemoradiation.

Chemotherapy

Patients receive simultaneous chemoradiation with 5-FU and oxaliplatin:

5-FU: 250 mg/m²/d as continuous intravenous infusion; d1-14 and d22-35

Oxaliplatin: 50 mg/m2 i.v., on the days 2, 9, 23, 30. Given as two hours bolus infusion in 500 ml Glucose 5%.

Deep regional hyperthermia (RHT)

Hyperthermia is scheduled twice weekly during the time of external radiotherapy and started within one hour before or after irradiation to a total of 10 treatments. The interval between two RHT-treatments has to be a minimum of 72 hours. Thermometry probes have to be positioned in the rectum (if accessible), the bladder, the vagina and the rima ani for continuous thermometry and thermal mapping of tumor-related temperatures. Therapeutic time starts when the tumor-related temperature in the rectum reached a minimum of 41.5°C or 30 min after enabling power. Therapeutic time is scheduled to be 60 min, the maximum total duration should not exceed 90 min.

Surgery

Curative resection will be tried 4-6 weeks after chemoradiation if no contraindications are present. Contraindications may be infiltration of the sacral vertebras 1 and 2 or infiltration of the basal pelvic muscles.

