5 TREATMENT

5.1 OVERVIEW

Radiotherapy (no prior pelvic irradiation):

45 Gy to the pelvis, once daily, 5 days a week for 5 weeks (25 x 1.8 Gy). If not resectable after 45 Gy, 3D-conformal boost to a total dose of 59.8 Gy.

Radiotherapy (prior pelvic irradiation):

45 Gy to the gross tumor volume with a security margin of 1 - 2 cm in each direction, once daily, 5 days a week for 5 weeks (25 x 1.8 Gy). If not resectable after 45 Gy, 3D-conformal boost to a total dose which is left to the discretion of the local radiotherapist.

Chemotherapy:

5-FU 250 mg/m²/d as continuous infusion, day 1-14 and day 22-35

Oxaliplatin 50 mg/m² i.v., d2, 9, 23, 30

Deep regional hyperthermia (RHT):

Twice weekly (minimum interval: 72 h) during the time of external radiotherapy and started within one hour before or after irradiation to a total of 10 treatments.

Surgery:

Curative resection (not part of the experimental study treatment) will be tried 4 - 6 weeks after chemoradiation.

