5.2.2 General information of the study medication

The relevant information on the drug characteristics, storage, application, mode of action and adverse reactions is included in the Summary of Product Characteristics (SmPC, "Fachinformation", appendix 6) for both drugs.

5.2.3 5-Fluorouracil

5-FU has been a widely used standard drug in the treatment of colorectal cancer for almost five decades. It is generally available under numerous brand names. An example SmPC ("Fachinformation") is included in Appendix 6, providing all required information on the drug.

5-FU is administered on the basis of milligrams of drug per square meter of body surface area (BSA) as measured at baseline, up to a maximum of 2 m², in a dose of 250 mg/m²/d as continuous infusion, day 1-14 and day 22-35.

Dose-limiting adverse effects of 5-FU include stomatitis, diarrhea and myelosuppression. Cardiotoxicity (chest pain similar to angina pectoris, arrhythmias, or even sudden cardiac death) are very rare events.

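### No blood count is scheduled between days 16 and 23, although the second 5-FU course starts on day 22 under a delay rule that depends on the count that day

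*Protocol*

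**What the plan says.** **Treatment days.** Section 5.1 gives "5-FU 250 mg/m²/d as continuous infusion, day 1-14 and day 22-35" and "Oxaliplatin 50 mg/m² i.v., d2, 9, 23, 30". The synopsis ("as continuous intravenous infusion; d1-14 and d22-35") and section 5.2.3 ("as continuous infusion, day 1-14 and day 22-35") repeat the 5-FU days. The second 5-FU course therefore starts on day 22, one day before the third oxaliplatin dose.

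**Assessment days.** Section 6.3 schedules blood count and chemistry "On day 1, 9, 16, 23, 30 of radiochemotherapy", and again at the end of treatment on day 35. The flow sheet in 6.1 uses the same days. Its extra column ("on day 9 + 23, additionally") and the matching entry in 6.3 ("In addition, on day 9 and 23") add only a neurological examination.

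**Delay rule.** Section 5.2.5.2 opens the rule with "If one of the following toxicity findings is still present on the day of the next chemotherapy administration". The list that follows includes leukopenia above grade 2 and thrombocytopenia above grade 1. Either one postpones therapy by at least a week, and therapy may start only once WBC exceeds 3000/µl and platelets exceed 100,000/µl.

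**The concern.** The rule needs to know the patient's counts on the day chemotherapy is due. At every other planned start the schedule supplies that information the same day or the day before. At the day-22 start it does not: the nearest counts are on day 16 and on day 23, when the infusion is already running.

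Two kinds of patient are affected. One has a delay-level cytopenia on day 16 and no scheduled check of recovery before day 22. The other has an acceptable count on day 16 and develops a silent cytopenia between then and day 22. The second falls under the rule only if it is read to cover newly arising findings as well as persisting ones. In both cases 5-FU could be started when the protocol's own criterion says it should be held. The issue is patient safety and uniform application of the delay rule across sites.

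**Working it through.** **Inputs.** Chemotherapy starts (5.1): 5-FU on days 1 and 22; oxaliplatin on days 2, 9, 23 and 30. Scheduled counts (6.1, 6.3): days 1, 9, 16, 23, 30 and 35. 5-FU dose: 250 mg/m² per day.

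**Age of the last scheduled count at each start** = start day minus the latest count day on or before it.

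| Planned start | Last count now | Age now (days) | Last count if day 23 moves to day 22 | Age then (days) |
|---|---|---|---|---|
| 5-FU, day 1 | day 1 | 0 | day 1 | 0 |
| Oxaliplatin, day 2 | day 1 | 1 | day 1 | 1 |
| Oxaliplatin, day 9 | day 9 | 0 | day 9 | 0 |
| 5-FU, day 22 | day 16 | 22 − 16 = **6** | day 22 | 0 |
| Oxaliplatin, day 23 | day 23 | 0 | day 22 | 1 |
| Oxaliplatin, day 30 | day 30 | 0 | day 30 | 0 |

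The maximum age falls from 6 days to 1.

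**Intervals between consecutive counts.** Now: 8, 7, 7, 7, 5 days. After the move: 8, 7, 6, 8, 5 days. The longest is 8 days in both.

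**5-FU given before the day-23 count**, taking one full infusion day:
- Course 2: 14 × 250 = 3500 mg/m²; 250 / 3500 = 7.1%.
- Both courses: 28 × 250 = 7000 mg/m²; 250 / 7000 = 3.6%.

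**Can another rule stand in for the missing count?** Section 5.3.2 withholds radiotherapy, and with it chemotherapy, at WBC below 1.0 × 10⁹/l (1000/µl) or platelets below 20 × 10⁹/l (20,000/µl). These limits are far below the recovery levels of 3000/µl and 100,000/µl in 5.2.5.2, and 5.3.2 schedules no count of its own.

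**Does the delay rule apply to 5-FU?** Section 5.1 lists 5-FU under chemotherapy. The dose table in 5.2.5.2 reduces 5-FU alone at grade 3 WBC or platelet toxicity, and it sets the dose for the following course. That course begins with 5-FU on day 22. Nothing restricts the rule to oxaliplatin days.

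**The case against.** The strongest reply is that the rule carries its own check. An investigator who saw a delay-level cytopenia on day 16 cannot establish recovery on day 22 without a new count, so the protocol obliges one even though the flow sheet does not list it. The rule is worded for persisting findings, so the new silent cytopenia needs a wider reading. That patient would have had an acceptable count on day 16 and no chemotherapy from day 15 to day 21, although radiotherapy continues. Exposure is about one day of an infusion that can be stopped. Patients attend radiotherapy five days a week (5.3.1), adverse events are recorded continuously with their CTC grade (6.7.2, 6.7.4), and extra tests are not forbidden. Finally, moving the count takes away the same-day result before day-23 oxaliplatin and leaves the formal toxicity assessment on day 23, although diarrhea and mucositis are also delay criteria.

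Much of this stands, and it keeps the point small. Symptomatic toxicity is largely covered by daily attendance and continuous recording, which is why only the laboratory criteria are at issue. The loss of the same-day count on day 23 is a real, small cost. The main reply does not remove the gap, however. An implied check is left to each site's habit in a multi-institutional trial, while the written schedule puts the sample one day after the start it should govern. A silent cytopenia can be seen only in a blood test.

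**Conclusion.** The point holds as a minor safety-alignment gap. Day 22 is the only planned chemotherapy start whose last scheduled count is more than one day old (6 days). Followed as written, the schedule lets about 250 mg/m² of 5-FU be given before a count that requires delay is seen. Oxaliplatin on day 23 is unaffected, because it has a same-day count.

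The conclusion assumes that the delay rule covers the start of 5-FU as well as oxaliplatin, and that the site takes no unscheduled count on days 17 to 22. Harm also requires a delay-level cytopenia that persists from day 16 or arises silently after it. The protocol gives no frequency for that, so the expected number of affected patients cannot be stated. No effect on the feasibility endpoint or the sample size is claimed.

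**What to change.** In the 6.1 flow sheet and in 6.3, move the blood count and chemistry from day 23 to day 22, and state that the result must be reviewed before 5-FU is started. A footnote to those two rows of the flow sheet is enough. Leave the physical examination, toxicity assessment and neurological examination on day 23, since the neurotoxicity table in 5.2.5.2 governs oxaliplatin.

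**Cost.** One sample moves by one day and the number of scheduled on-treatment counts stays at 6. Day 22 is already a treatment day. The count before day-23 oxaliplatin becomes one day old, as it already is for day-2 oxaliplatin. The interval to the day-30 count rises from 7 to 8 days, equal to the present longest interval (day 1 to day 9).

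**Alternative.** If a same-day count before day-23 oxaliplatin is to be kept, add a day-22 count instead. That costs one extra sample per patient (7 instead of 6).

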6.7.2 Toxicity / adverse events (AE)

Adverse events (AE):

An adverse event (AE) is any untoward medical occurrence in a subject or clinical investigation subject administered a pharmaceutical product and which does not necessarily have a causal relationship with this treatment.

An AE can therefore be any unfavourable and unintended sign (including an abnormal laboratory finding, for example), symptom, or disease temporally associated with the use of a medicinal product, whether or not considered related to the medicinal product.

Due to regulatory requirements, events occurring during pre- and post-treatment periods should also be designated as AEs. Therefore, safety surveillance - reporting of (S)AEs - commences at the time when the subject is enrolled into the study (date of signature of the informed consent) until the End of Treatment Visit has been performed. Therefore events occurring in the period between the signed informed consent and beginning of the study drug administration are to be designated as AEs.

Adverse drug reaction (ADR):

All noxious and unintended responses to a medicinal product related to any dose should be considered adverse drug reactions (ADR). The phrase "responses to a medicinal product" means that a causal relationship between a medicinal product and an AE is at least a reasonable possibility i.e. the relationship cannot be ruled out.

Pre-existing diseases, when worsening during study therapy, have to be considered as adverse events. They can lead to serious adverse events, if they meet the criteria described in section 6.7.3.

All adverse events and toxicities are recorded continuously and reported in the Toxicity Form of the CRF (cf. section 6.7.4 for details).

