- Other action (none, concomitant medication given, new or prolonged hospitalization, procedural surgery, chemotherapy delayed, chemotherapy discontinued, chemotherapy dose reduction).
- The outcome according to the following definitions:

Recovered with sequelae.

Recovered without sequelae.

Ongoing, no therapy.

Ongoing, therapy.

Died.

Change in toxicity grade/severity.

• It must be indicated whether the SAE is the leading event, i.e. the primary medical reason for SAE reporting.

If in any one subject the same AE occurs on several occasions, then the AE in question must be documented and assessed anew each time.

Serious adverse events will be collected for 30 days after the last dose of study treatment. Serious adverse events occurring more than 30 days after a patient is discontinued from the study treatment will NOT be reported unless the investigator feels that the event may have been caused by the study drug or a protocol procedure.

6.7.5 **Procedure for reporting serious adverse events**

In the event of the occurrence of any clinical AE or abnormal laboratory test value that is serious (according to the definition provided in section 6.7.3) during the course of the study or the immediate post-treatment period, irrespective of the treatment received by the subject, the investigator is obliged to inform the investigator-sponsor **within 24 hours** by phone or fax:

[name] (LKP) Univ. Hospital Erlangen Dept. of Radiation Oncology [name] [name] Germany [contact] [contact] Email: [contact]

The immediate report by the investigator to the investigator-sponsor shall be followed by detailed, written reports using the SAE report form. The immediate and follow up reports shall identify subjects by unique code numbers assigned to the latter.

All SAEs have to be reported on the standard toxicity form of the CRF as well as on the specific SAE form including all required details.

The investigator-sponsor of the study will ensure that the legal requirements for reporting adverse events to the respective federal agency ("Bundesoberbehörde", BfArM bzw. PEI [Paul-Ehrlich-Institut]) as well as to the responsible ethical comitee(s), according to §12, Abs. 6 and § 13, Abs. 1 to 7 of GCP-V, are fulfilled.

The sponsor is obliged to inform the participating investigators about SUSARs (cf. section 6.7.3 for definition), according to the German regulations (§11, Abs. 2 and 3 of GCP-V).

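### The end-of-treatment visit and the AE cut-off are dated day 35, before any radiotherapy boost starts, so no toxicity check or blood count is scheduled during or at the end of the boost

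*Protocol*

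**What the plan says.** - **Visit date.** The flow sheet in section 6 heads the column "end of treat- ment, day 35". Section 6.3 lists the same visit as "At the end of radiochemotherapy (day 35"). It includes CTC toxicity, a blood count, serum chemistry and tumour imaging.
- **AE reporting period.** Section 6.7.2 starts (S)AE reporting at consent and continues it "until the End of Treatment Visit has been performed". The same section adds: "All adverse events and toxicities are recorded continuously and reported in the Toxicity Form of the CRF".
- **SAE period.** Section 6.7.4 differs: "Serious adverse events will be collected for 30 days after the last dose of study treatment".
- **Boost.** Under 5.3.1, patients whose tumour is judged not resectable after 45 Gy receive a boost. Without prior pelvic irradiation it is given with a margin in every "direction to a total dose of 59.8 Gy, at least". With prior irradiation the total dose is left to the local radiotherapist.
- **Blood counts as a treatment rule.** Section 5.3.2 says "RT will also be withheld for WBC", neutrophil and platelet values below set limits, and makes no exception for the boost.
- **DLT.** Section 6.7.1 counts any grade 3 or 4 thrombocytopenia, any grade 3 or 4 non-haematological toxicity except nausea, and grade 3 or 4 leukopenia or neutropenia that is complicated or lasts more than 7 days. It sets no time window.
- **Primary endpoint.** Under 7.2.1 a patient fails feasibility through a DLT, premature withdrawal from radiochemotherapy, or hyperthermia delivery below 80%.

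**The concern.** DLT is the core of the primary endpoint, and the boost is part of protocol radiotherapy. If the last on-treatment assessment and the stated end of AE reporting both come before the boost, a DLT that first appears in the boost has no dedicated occasion on which to be found. The error runs one way: an unseen DLT can turn a failure into a success but never the reverse, so it favours accepting the regimen. It affects the patients who receive the highest dose within this course. Sections 6.7.2 and 6.7.4 also give two different end points for SAEs, so a site cannot follow both as written.

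**Working it through.** **Inputs.** 25 fractions of 1.8 Gy, once daily, five days a week (5.3.1); boost to at least 59.8 Gy without prior irradiation (5.3.1); checks on days 1, 9, 16, 23, 30 and 35 (section 6, 6.3); surgery 4 to 6 weeks after chemoradiation (5.5); follow-up every 3 months at first (6.1). Assumptions: radiotherapy starts on day 1 without interruption, and boost fractions are 1.8 or 2.0 Gy (the protocol gives no boost fraction size).

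**Base course.** 25 × 1.8 Gy = 45 Gy, and 25 / 5 = 5 weeks, as the protocol states.

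**Boost length.** 59.8 − 45 = 14.8 Gy. 14.8 / 1.8 = 8.22, so 9 fractions. 14.8 / 2.0 = 7.4, so 8 fractions.

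**Calendar, weekdays only.**

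| Start | Fraction 25 | First boost fraction | Last of 8 | Last of 9 |
|---|---|---|---|---|
| Monday | day 33 | day 36 | day 45 | day 46 |
| Tuesday | day 35 | day 36 | day 45 | day 46 |
| Wednesday | day 35 | day 36 | day 45 | day 48 |
| Thursday | day 35 | day 36 | day 47 | day 48 |
| Friday | day 35 | day 36 | day 47 | day 48 |

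The boost starts no earlier than day 36 whatever the starting weekday. It ends 45 − 35 = 10 to 48 − 35 = 13 days after the day-35 visit. For pre-irradiated patients the start is the same, but the end cannot be worked out because the dose is discretionary.

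**Next scheduled assessment.** If a boosted patient has surgery 28 to 42 days after the boost, it falls between day 45 + 28 = 73 and day 48 + 42 = 90. The post-surgery toxicity assessment is therefore at least 73 − 35 = 38 days after day 35. Without surgery, the next one is the first 3-monthly follow-up visit. The flow sheet shows no blood count or serum chemistry at either.

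**What other rules already catch.**
- Serious events: even if the last dose in 6.7.4 means the last 5-FU day, collection runs to day 35 + 30 = 65, past the end of a boost on day 45 to 48.
- Severe diarrhea: under 5.6.3 these patients "must be hospitalized", and in-patient hospitalization makes the event serious (6.7.3).
- Grade 4 clinical events: graded as life-threatening or disabling (6.7.4), so mostly serious.

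**What is left.** Non-serious grade 3 clinical events other than severe diarrhea that resolve before the next visit, and DLTs visible only in the laboratory, such as grade 3 thrombocytopenia.

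**Effect on the rate.** Each patient wrongly counted as feasible among 59 adds 1/59 = 1.7 percentage points. The number of such patients cannot be derived: the protocol gives neither the share who are boosted nor the share of boost DLTs that would be missed.

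**The case against.** The strongest reply is that a missing visit is not missing capture. Section 6.7.2 requires continuous recording and says that post-treatment events count as AEs. Section 6.7.4 requires every AE to be graded in the CRF, and 6.7.6 requires follow-up of AEs until the end of study visits. The visit is named by an event, the end of radiochemotherapy, and day 35 is also the last 5-FU day, so it can be read as the nominal date of an unboosted course. The count limits in 5.3.2 can be applied only if somebody takes counts.

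Much of this stands. A reader might infer that boost toxicity is never assessed on schedule. That goes too far, because CTC toxicity is assessed after surgery and at each follow-up visit. A reader might also infer that AE capture certainly stops at day 35. The text does not establish that, since the same section points both ways and the CRF is not shown.

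The reply does not close the gap. The sentence on continuous recording stands in the section that ends reporting at the visit. No recording instruction reveals a low platelet count if no blood is drawn. Section 5.3.2 implies counts but schedules none. No alternative visit is named for boosted patients, and the imaging on day 35 would suit the decision on resectability after 45 Gy, which is taken before the boost.

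It is also fair to say that the absence of counts after day 35 applies to every patient, so the boost does not cause it. It matters more where radiotherapy continues.

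**Conclusion.** The point holds in limited form. The visit date and the 6.7.2 cut-off, followed literally, precede the end of protocol radiotherapy for boosted patients. No toxicity check or blood count is scheduled during or at the end of the boost, 6.7.2 contradicts 6.7.4 on SAEs, and 6.7.1 leaves the DLT window open. Transient non-serious grade 3 events and laboratory-only DLTs may go unrecorded.

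A reader might infer that every missed DLT turns a patient into a success. Under 7.2.1 that is so only when the missed event is the patient's sole failure. A patient with an earlier DLT, premature withdrawal or too little hyperthermia remains a failure.

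A reader might also want to convert the gap into an inflated type I error. The documents do not support this, because any assumed number of missed patients would be freely chosen. The direction is upward; the amount is unknown.

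The start on day 36 assumes uninterrupted weekday treatment from day 1. The end on day 45 to 48 also needs the assumed fraction sizes and applies only to patients without prior pelvic irradiation. The 19/59 two-stage design is not affected.

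**What to change.** - In 6.1 and 6.3, define the end-of-treatment visit as the visit after the last radiotherapy fraction, boost included, with day 35 as the nominal date for patients without a boost.
- In 6.7.1 and 6.7.2, run DLT and AE capture to 30 days after the last study treatment, and state that the boost counts as study treatment. This brings 6.7.2 into line with 6.7.4.
- Continue the existing toxicity and blood count checks through the boost, at roughly the weekly spacing already used.

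The cost is a short amendment and one or two extra routine checks for each boosted patient. The sample size and decision rule do not change.
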